6.1.2 Handling of Dropouts and Missing Data

6.1.2.1 Dropouts

Subjects who complete the Day 0 procedures but withdraw prior to the Follow-up Period will not be replaced

6.1.2.2 Missing Data

All analysis will be based on available data to summarize safety and efficacy results. However, a conservative approach to partial dates and missing adverse event's relationships will be as follows:

- For the OS analyses, if a subject's death month and year are provided but the day is missing, the day will be set to the first day of the month, unless other qualifying study data support survival until a later date in the same month. The same concept will be applied if only the year is known. For a completely missing date of death, the fatality will be imputed to have been occurred on the last available contact of the subject where we still know he/she was alive.
- Adverse events with partial dates with the same month and year as the Procedure Day 0 will be considered as treatment-emergent adverse events.
- If an adverse event's relationship is missing it will be assumed to be related.

6.1.3 Pooling of Investigator Sites

Data will be pooled from centers for these analyses. The justification for pooling is made on a clinical basis (Meinert, 1986). The basis for pooling comes from three critical factors: 1) The study sites must implement one common protocol. 2) The sponsor must provide very close monitoring of study site compliance. 3) The study sites must use common data collection procedures.

However, region (EU and US, China, Korea, other) will be included as a factor in supportive and exploratory CPH analyses for OS and PFS, as well as safety analyses.

6.1.4 Determination of Sample Size

The study is designed to detect with 80% power a hazard ratio for OS of 0.67 (33% risk reduction) in the ThermoDox (TR) arm compared with the control (PR) arm with an overall 1-sided type 1 error of 0.025. An OS hazard ratio of 0.63 was observed among Celsion's initial phase III trial, the HEAT study (Protocol 104-06-301) subjects with a solitary 3-7 cm lesion treated with \geq 45 minutes of RFA. A 3%/year loss to survival follow-up rate has been assumed and using a 1:1 treatment allocation (TR:PR) of 550 subjects, a target of 197 events (deaths) will be required for the primary analysis.

Based on these design operating characteristics and assuming a median survival time of approximately 4.5 years in the control arm, the primary analysis target events milestone will be reached approximately 30 months after the last subject is randomized in the study. The median OS in the control arm was estimated based on the interim OS results in the HEAT study.

6.2 Subject Disposition, Baseline and Treatment Characteristics

6.2.1 Subject Disposition

The number of subjects in each study population and the reasons for exclusion, along with any randomization and/or stratification errors will be summarized by treatment arm. In addition, subjects that discontinue study treatment or study follow-up will also be summarized, along with reasons for study discontinuation.

The number of screening failures, and the reason, will be tabulated.

6.2.2 Protocol Deviations

CSR Reportable

A CSR reportable Protocol Deviation is related to inclusion/exclusion criteria, conduct of the trial, patient management or patient assessments that impact the safety of the subjects or jeopardize the quality of the study data.

The following classifications will be used to report CSR reportable Protocol Deviations:

- RD1 - A subject that did not meet entry criteria
- RD2 - A subject that developed withdrawal criteria but was not withdrawn
- RD3 - A subject that received the wrong treatment or incorrect dose
- RD4 - A subject that received an excluded medication
- RD5 - Critical ICF, GCP and other Protocol Deviations

Major CSR Reportable Protocol Deviations

In addition, among all CSR Reportable Protocol Deviations, a set of “major protocol deviations” is defined as a means to measure adherence to key aspects of the protocol using prespecified sensitivity analyses.

A summary of all major protocol deviations (at study entrance and during the study period) by type of deviation will be provided.

A patient will be classified as having a major protocol CSR reportable deviation if she/he meets at least one of the criteria presented below.

MRD1 - No HCC lesions

MRD2 - single HCC lesion < 3.0 or > 7.0 cm or multiple lesions

- MRD3 - ECOG performance status at baseline not 0
- MRD4 - Not a Child-Pugh A classification
- MRD5 - baseline platelets < 75,000/mm³
- MRD6 - RFA start time > 20 minutes from start of infusion
- MRD7 - RFA dwell time < 45 minutes

CSR Non-Reportable

A CSR non-reportable Protocol Deviation may be important to address and document as part of site management and oversight, but will not be considered reportable in the CSR.

The following classifications will be used to capture non-reportable PDs.

- NRD1 - SAE reporting
- NRD2 - Informed consent (other than those captured above)
- NRD3 - Study procedures

NRD4 - Investigational product (other than incorrect dose or wrong treatment)

6.2.3 Subject Baseline Characteristics

Demographic data (age, race, gender) will be summarized by treatment arm for the ITT and AT population.

Subject characteristics such as height (in cm), weight (in kg), ECOG performance and disease history reported at the Screening/Baseline visit will be summarized by treatment arm for the ITT population.

Data listings will present the demographic and baseline characteristic data.

6.2.4 Treatment Exposure and Compliance

The study treatment administration and compliance profile will be summarized descriptively by treatment arm for the AT population and displayed in data listings.

6.2.5 Prior and Concomitant Medications and Therapies

Prior and concomitant medications will be coded according to the World Health Organization (WHO) Medication Dictionary for Concomitant Medication.

Prior and concomitant medications will be summarized descriptively by treatment arm for the ITT population and displayed in data listings.

6.2.6 Medical Histories

Medical history including cancer and non-cancer history data listing will be presented by treatment arm for the ITT population.

6.2.7 Follow-up Period

Duration of Follow-up for Survival:

A summary table showing the duration of follow-up will be presented by treatment arm for the ITT population. The follow-up period is defined as the time starting on the date randomized until the last day of contact, or the day of withdrawal from study or the day of death, whichever occurs last.

Non-study anti-cancer treatment during follow-up period:

Patients receiving non-study anti-cancer treatments initiated during the follow-up period will be summarized in a table by treatment arm. The table will display the number, type and time to starting a new non-study anti-cancer treatment. The summary table will also show the number of patients starting a new anti-cancer treatment without having experienced documented radiological progression by the investigator. The time to start of the new anti-cancer treatment will be defined as the start date of the new anti-cancer therapy minus the date of last dose of study medication + 1. If the start date of the new anti-cancer treatment is missing, the time to start of anti-cancer therapy will be missing for that patient.

6.3 Efficacy Analysis

6.3.1 Primary Efficacy Variable(s)

Overall survival will be measured by time (in months) from randomization to death from any cause or the end of the study. Subjects who have not died will be censored at the date of last study follow-up, or the cut-off date, whichever is earlier as mentioned in Section 3.

The OS cut-off date used for the primary analysis will be based on the observations of the 197th death in the study. All patients dying on the calendar date of the 197th death will be included in the analysis should more than one patient die on the calendar date of the 197th death. Patients having a documented survival status (alive or dead) after this date are censored at the cut-off date.

With the OS cut-off date being event driven, for operational efficiency, the cut-off date for all other study endpoints (e.g., PFS) will be fixed at close proximity of the OS cut-off date, when the milestone is nearing completion. This especially applies to the interim analyses.

OS in the ITT population will be compared between the 2 treatment arms using the stratified log-rank test (Score statistic from PHREG and ties=Breslow (Kalbfleisch and Prentice 1980)). The estimate of the hazard ratio and corresponding 95% CI will be provided using a Cox proportional hazards (CPH) model including treatment and the stratification factors (maximum lesion diameter [3-5 cm versus >5-7 cm] and RFA route [laparoscopic, open surgical, percutaneous]) in the model. The survival curves will be estimated using Kaplan-Meier estimates. The stratification factors will be populated as per the randomization assignment.

Survival for each arm will be summarized using Kaplan Meier curves and is further characterized in terms of the median and survival probability at 12, 24, 36, 48, 60 and 72 months, along with the corresponding 2-sided 95% confidence intervals for the estimates. Confidence intervals for median survival are based upon the methods of (Brookmeyer and Crowley 1982). In addition to Kaplan-Meier estimates, corresponding 2-Sided 95%

confidence intervals constructed using the Clopper-Pearson approximation to the exact binomial proportion (Hollander and Wolfe 1973).

For the first interim analysis, if there are more than 129 events (118+10%), an additional table will be presented for sensitivity purposes, based only on the first 118 events. The same principle applies for the second interim analysis, accordingly.

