1. PROTOCOL SYNOPSIS

Title of Study	A Phase III, Randomized, Double Blind, Dummy-Controlled Study of ThermoDox® (Lyso-Thermosensitive Liposomal Doxorubicin-LTLD) in Hepatocellular Carcinoma (HCC) using standardized Radiofrequency Ablation (RFA) treatment time \geq 45 minutes for solitary lesions \geq 3 cm to \leq 7 cm.
Protocol Number	104-13-302
Countries	Global
Study Centers	Up to 100 Centers
Study Period	Approximately 36-month enrollment with estimated 5-year follow up
Clinical Phase	Phase III
Objectives	
The primary objective is to compare overall survival (OS) between patients receiving RFA plus ThermoDox versus RFA alone, using a standardized Radiofrequency Ablation (sRFA) treatment dwell time \geq 45 minutes.
 
The secondary objectives are to compare progression-free survival (PFS) and safety between patients receiving sRFA plus ThermoDox versus sRFA alone, using a standardized treatment dwell time \geq 45 minutes.

Study Design	
This is a randomized, double blind, dummy controlled multicenter trial to evaluate the efficacy and safety of ThermoDox plus sRFA compared to sRFA alone using standardized treatment dwell time \geq 45 min. for solitary HCC lesions \geq 3.0 cm to \leq 7.0 cm. An sRFA treatment for this protocol is defined as the dwell time of \geq 45 minutes measured from the first activation of the RFA probe to produce coagulative necrosis of target tissue through removal of the RFA probe after the final ablation cycle or deployment. This includes the multiple ablation cycles and repositioning time between cycles for an individual patient.
 
Eligible HCC patients will have a solitary lesion not amenable to curative resection consistent with clinical diagnosis of AASLD classification guidelines and will be candidates for RFA. Subjects will be randomly assigned to receive either standardized sRFA plus ThermoDox at 50 mg/m² or standardized sRFA plus a dummy infusion using a standardized RFA dwell time \geq 45 minutes. Randomization and analysis will be stratified by maximum lesion diameter (3-5 cm versus $>$ 5-7 cm) and RFA route (laparoscopic, open surgical, percutaneous).
 
Screening Period
 
Subjects will be evaluated up to 21 days prior to the RFA procedure date to establish eligibility for study treatment. Subjects must meet all the study inclusion/exclusion criteria prior to randomization to a treatment arm.

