7.4 End of the Study

The primary analysis will be based on the first 197 events (deaths) observed. Survival follow-up will be continued for 5 years after the last patient is randomized, to enhance OS evidence for regional or other subgroup assessments.

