6.3.3 Secondary Efficacy Variable(s)

PFS will be measured from the date of randomization to the first date on which one of the following occurs, as determined by CT or MRI scan:

- Death of any cause
- Treatment failure (inability to achieve Complete Response (CR) after two RFA \pm ThermoDox treatment sessions)
- Progression due to local tumor recurrence after initial CR

- Progression due to distant intrahepatic tumor recurrence
- Progression due to extrahepatic tumor recurrence

All secondary endpoints comparisons will be made at the 2-sided 0.05 significance level for the ITT population. Since PFS is the only secondary endpoint for regulatory registration purposes, no further multiplicity adjustments will be made. Assuming that OS demonstrates significance at the 1-sided 0.025 level, PFS can subsequently be tested at the 1-sided 0.025 level.

PFS will be analyzed with methodology applied to the OS endpoint. Specifically, PFS will be analyzed with the methodology specified in Section 6.3.1 and the supportive analyses in Section 6.3.2.

In line with FDA guidance (Clinical Trial Endpoints for the Approval of Cancer Drugs and Biologics, 2007), several sensitivity analyses for Progression-Free Survival are also conducted on the ITT Population as follows:

- Analysis that includes clinical progression as a PFS event in addition to the presence of radiological evidence of progression.
- Analysis including clinical progression as a PFS event that also counts initiation of non-study antitumor therapy as an event date rather than as date used to censor subsequent response assessments. (ITT population)
- An analysis that includes all death and response assessments (without censoring missed visits) and also counting as an event, clinical progression, the initiation of anti-tumor therapy or death through the date of cut-off for survival (ITT population)
- Analysis using the next scheduled visit as the event date for radiological progression when image assessment falls more than 1 month after a scheduled assessment. If reassignment of the progression date to the next scheduled visit results in a progression date after death, the death date is used as the event date. (ITT population)
- Kaplan-Meier curves of time to first, second, third, fourth and fifth radiological tumor assessments from date of randomization are done and compared between groups using the log-rank test. (ITT population)

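### SAP 6.3.1 gives Kaplan-Meier survival rates Clopper-Pearson intervals, with no denominator and no allowance for censoring

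*SAP*

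**What the plan says.** SAP 6.3.1 summarises survival in each arm by Kaplan-Meier curves, the median, and survival probabilities at 12, 24, 36, 48, 60 and 72 months, "along with the corresponding 2-sided 95% confidence intervals for the estimates". Brookmeyer-Crowley is assigned to the median only. The next sentence begins "In addition to Kaplan-Meier estimates, corresponding 2-Sided 95" and names "confidence intervals constructed using the Clopper-Pearson approximation to the exact binomial proportion". It has no main verb.

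The same section censors living subjects at last follow-up or at the cut-off. It gives no binomial denominator and no rule for subjects censored before a landmark. Neither document names Greenwood's variance or any other variance that allows for censoring.

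The method reaches further than the final OS table. SAP 6.3.3 states that "PFS will be analyzed with methodology applied to the OS endpoint". SAP 6.3.1 also refers to interim output: "if there are more than 129 events (118+10%), an additional table will be presented for sensitivity purposes".

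**The concern.** A Clopper-Pearson interval takes x successes out of n subjects whose outcome at the time point is known for all. At the late landmarks many subjects have not been followed that long, so their status there is unknown. The Kaplan-Meier estimate handles this by using the changing risk set, and its variance must do the same.

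The SAP leaves n open, and the direction of the error depends on it:

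- **All subjects in the arm:** late intervals are too narrow.
- **Number at risk:** intervals are too wide.
- **Known-status subjects only, or censored subjects counted as alive:** the interval is centred on the wrong value.

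Late survival rates for the primary endpoint would then either lack 95% coverage or depend on a programming choice that nobody has recorded.

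**Working it through.** **Inputs.** SAP 6.1.4: 550 subjects at 1:1 (275 per arm), control median 4.5 years (54 months), HR 0.67, 3% loss per year, 197 deaths, milestone "will be reached approximately 30 months after the last subject is randomized in the study". Protocol synopsis: "Approximately 36-month enrollment with estimated 5-year follow up". The planned cut-off is therefore month 36 + 30 = 66. Assumptions not in the documents: exponential survival and uniform accrual.

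**Step 1: reproduce the plan's event target.** Schoenfeld: 4 × (1.960 + 0.842)² / (ln 0.67)² = 4 × 7.849 / 0.16038 ≈ 196, against 197 stated. Power at 197 deaths is 80.2%. Expected deaths are 186 at month 60 and 206 at month 66, so the 197th falls near month 63, slightly before the planned month 66.

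**Step 2: one arm at month 66.** Control arm, n = 275, 3,000 simulated replicates. True S(t) = exp(−ln 2 × t/54). The last three columns give mean width / coverage of the 95% interval.

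| Month | True S | Censored before t | At risk | Greenwood log-log | Clopper-Pearson, n = 275 | Clopper-Pearson, n = at risk |
|---|---|---|---|---|---|---|
| 36 | 0.630 | 47 | 132 | 0.118 / 95.1% | 0.117 / 94.8% | 0.171 / 99.6% |
| 48 | 0.540 | 98 | 66 | 0.132 / 95.2% | 0.121 / 92.9% | 0.251 / 100% |
| 60 | 0.463 | 139 | 18 | 0.163 / 95.4% | 0.121 / 85.4% | 0.482 / 100% |

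- **n = 275:** shortfall is 1 − 0.121/0.132 = 8% at 48 months and 1 − 0.121/0.163 = 26% at 60.
- **n = at risk:** ratio is 0.251/0.132 = 1.9 at 48 months and 0.482/0.163 = 3.0 at 60.
- **Censored counted as alive:** the point value is 0.594 against 0.540 at 48 months (coverage 59.5%), and 0.571 against 0.463 at 60 (coverage 5.9%).
- **Known status only:** at 48 months, 66/(275 − 98) = 0.373, which is 0.167 too low.

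The mechanism shows in the effective sample size, n_e = (1 − S)/(S × G), where G is the Greenwood sum. It is about 257, 217 and 145 at 36, 48 and 60 months. Using 275 at 60 months claims precision the data do not have: √(145/275) = 0.73.

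**Step 3: both arms at the primary cut-off.** Trials were simulated with the cut at the 197th death (median month 63) and at fixed month 66, 4,000 runs each.

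- At the 197th death, about 40% (control) and 46% (ThermoDox) are censored before month 48, and about 54% and 64% before month 60.
- Over both cuts, n = 275 is 8-13% too narrow at 48 months (coverage 91-93%) and 25-32% too narrow at 60 (coverage 83-86%).
- The number at risk gives 1.7-2.0 times the Greenwood width at 48 months and 2.7-3.4 times at 60.
- At the 197th death, known-status-only is centred about 0.20 too low at 48 months. Counting censored subjects as alive is 0.05-0.07 too high.
- At the 197th death, the 60-month figures use the 80-81% of runs with someone still at risk (mean 14 control, 18 ThermoDox). Follow-up reaches 72 months in under 1% of runs.

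**Step 4: other analyses, n = 275.**

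| Analysis | Landmark | Too narrow by | Coverage |
|---|---|---|---|
| 118 deaths (about month 42) | 24 months | 12% | 90-91% |
| 118 deaths | 36 months | 31% | 82-83% |
| 158 deaths (about month 52) | 36 months | 12-13% | about 92% |
| 158 deaths | 48 months | 32-33% | 83-85% |
| Month 96 (36 + 60) | through 60 months | at most 2% | near nominal |
| Month 96 | 72 months | 5% | near nominal |

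The 48-month figure at 158 deaths rests on about nine runs in ten, those with a subject still at risk. Month 96 follows from Protocol 7.4: "Survival follow-up will be continued for 5 years after the last patient is randomized". At that point 61 control and 82 ThermoDox subjects remain at risk at 72 months.

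**Step 5: PFS.** The documents give no PFS median. With assumed control medians of 12 to 24 months, HR 0.67 and a cut at month 63.3, n = 275 is 13-16% too narrow at 48 months, with coverage around 90%.

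**The case against.** The strongest reply is that the sentence can be read differently. The section has already promised intervals for the survival probabilities, so the Clopper-Pearson clause may only add a crude binomial interval beside a standard Kaplan-Meier one. The wording allows this. But then the Kaplan-Meier intervals have no stated method, and the crude proportions still lack a denominator and a censoring rule. The same sentence needs rewriting on either reading.

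A second reply is that SAP 6.1.1 has a default denominator, the arm's population size. That rule is written for percentages in summary tables of categorical variables. It does make n = 275 the likeliest choice and the more extreme alternatives less likely. But n = 275 is the choice that under-covers at late landmarks.

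Third, the effect is limited. This stands. At the primary cut-off nothing material changes through 36 months, few subjects are left at 60, and the error nearly vanishes by month 96. The interim figures apply only if the landmark summary is run then, and the PFS figures rest on assumed medians. No decision rule in the SAP uses a landmark interval.

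Finally, log-log Greenwood is not the only cure. Clopper-Pearson with the Greenwood-based effective n covered 95.7-96.2% at 36 to 60 months. That also stands.

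**Conclusion.** The concern holds and should be fixed. Followed as written, with the likeliest denominator, the method gives 60-month OS intervals a quarter to a third too narrow at the primary analysis, with 83-86% coverage instead of 95%. At 48 months the shortfall is 8-13%. Other readings of n give intervals up to about 3.4 times too wide, or centred on the wrong value.

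The damage is confined to descriptive landmark estimates. The stratified log-rank test, Cox hazard ratio, alpha spending, 197-death target and Brookmeyer-Crowley median interval are untouched. The sizes rest on exponential survival and uniform 36-month accrual; the remaining OS inputs are the plan's own. That the method ignores censoring does not depend on those assumptions.

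**What to change.** Replace the Clopper-Pearson sentence in SAP 6.3.1 with: *Pointwise 95% CIs for Kaplan-Meier survival probabilities will use Greenwood's variance with the complementary log-log transformation.* State that it applies to OS and PFS at every analysis.

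Add that a landmark is reported only where subjects remain at risk. The 72-month landmark is not expected to be estimable at the primary cut-off but should be at the later 5-year follow-up analysis.

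If the sponsor prefers to keep Clopper-Pearson, the SAP must define n as the Greenwood-based effective sample size.

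The cost is one SAP sentence and the matching program option. Design, sample size and testing do not change.

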6.3.2 OS Supportive Analyses

Supportive analyses for OS, conducted in the ITT population (unless otherwise noted), will include:

- a. The unstratified log-rank test and a CPH model (only treatment effect in the model).
- b. Multivariate analysis using the CPH model, including the stratification factors and the following set of potential prognostic/predictive factors: age (< 65 v. \geq 65), race (Caucasian, Asian, Other), region (EU and America, China All, Korea, Other), RFA start time, RFA dwell time (< 90 min, \geq 90 min), device, disease etiology (Hep B, Other), ECOG Performance Status (0, 1, 2, 3, 4, 5), Alfa-feto protein >200 ng/mL (yes/no).
- c. Factors included in the model will be assessed for co-linearity and a stepwise selection process will be applied to identify a final subset of prognostic/predictive factors in the model. Once the subset has been established, treatment will be added to the final model to assess its effect. An exploratory analysis of treatment by factor interactions using the CPH model will be conducted, using the factors identified in the final model above.
- d. Subgroup analyses will also be conducted for the stratification factors and the potential prognostic/predictive factors identified in Section 6.33.b above. The HR and associated 95% CI will be presented for each subgroup.
- e. The primary efficacy analysis, as outlined in Section 6.3.1, will also be run excluding any subjects that met the Major CSR Reportable Protocol Deviation criteria MRD1 to MRD7 as outlined in Section 6.2.2.
- f. A stratified log-rank test using the final strata as recorded on the CRF, in the event there are differences from the primary IVRS assignments. (AT population)
- g. Additional exploratory analyses may be performed.

In addition, a study follow-up Kaplan-Meier analysis (as for OS) will be presented for all subjects. Subjects will be censored if they have died, on their date of death. Only median, 25th and 75th percentiles will be presented.

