15.3.2.2 OS - Supportive Analyses

Supportive analyses for OS, conducted in the ITT population (unless otherwise noted), will include:

- a. The unstratified log-rank test and a CPH model (only treatment effect in the model).
- b. Multivariate analysis using the CPH model, including the stratification factors and the following set of potential prognostic/predictive factors: age (< 65 v. ≥ 65), race (Caucasian, Asian, Other), region (EU and US, China, Korea, Other), baseline platelets, RFA start time, RFA dwell time (≤ 45 min – for any outliers, ≥ 45 min and ≤ 90 min, ≥ 90 min), device, disease etiology (Hep B, Other).

Factors included in the model will be assessed for co-linearity and a stepwise selection process will be applied to identify a final subset of prognostic/predictive factors in the model. Once the subset has been established, treatment will be added to the final model to assess its effect.

An exploratory analysis of treatment by factor interactions using the CPH model will be conducted, using the factors identified in the final model above.

- c. Subgroup analyses will also be conducted for the stratification factors and the potential prognostic/predictive factors identified in Section 15.3.2.2.b above. The HR and associated 95% CI will be presented for each subgroup.
- d. The primary efficacy analysis, as outlined in Section 15.3.2.1, will also be run excluding any subjects that did not meet key eligibility criteria: a) single HCC lesion between ≥ 3.0 and ≤ 7.0 cm, b) ECOG performance status, c) RFA start time within 20 minutes of starting the infusion, d) RFA dwell time ≥ 45 minutes, and e) baseline platelets $\geq 75,000/\text{mm}^3$ and f) Child-Pugh A classification. Additional sensitivity analyses will be defined in the SAP.

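### Supportive OS and PFS analyses run under an ITT label adjust for, and subgroup by, RFA start and dwell time, which are set only after randomisation

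*SAP*

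**What the plan says.** SAP 6.3.2 places the supportive OS analyses in the ITT population by default. Only item f names another population (As-Treated).

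- **Item b** lists "RFA start time, RFA dwell time" among the candidate prognostic or predictive factors for a Cox model. Dwell time is split at 90 minutes; start time has no cut-points.
- **Item c** applies stepwise selection to the list and then says: "Once the subset has been established, treatment will be added to the final model to assess its effect". Treatment-by-factor interactions follow and are called exploratory.
- **Item d** gives a hazard ratio and confidence interval within subgroups of the same factors.
- **Item e** repeats the primary analysis "excluding any subjects that met the Major CSR Reportable Protocol Deviation criteria MRD1 to MRD7". In SAP 6.2.2, MRD1-5 describe the subject at entry (lesion, ECOG, Child-Pugh class, platelets). MRD6 is an RFA start more than 20 minutes after the infusion began, and MRD7 is a dwell time under 45 minutes.

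Protocol 15.3.2.2 has a similar list, including "baseline platelets, RFA start time, RFA dwell time", and its exclusion analysis counts the two RFA times among eligibility criteria. SAP 6.3.3 applies the 6.3.2 analyses to PFS. SAP 6.1.2.2 says analyses use the data available and has no rule for missing RFA times.

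**The concern.** An ITT comparison is protected by randomisation only while it conditions on nothing that treatment could have influenced. RFA start and dwell time are measured after assignment and after the infusion has started. If either arm's treatment changes whether, when or for how long a subject is ablated, groups formed on those variables are no longer comparable between arms. Adjusting for them can remove part of the treatment effect or introduce a spurious one. Subjects never ablated have no value, so a complete-case fit drops them from an analysis still called ITT.

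At stake is how the supporting evidence is read. An adjusted hazard ratio and a forest plot headed ITT will be taken as randomised comparisons, and the dwell-time rows will attract attention because dwell time is the premise of the trial.

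**Working it through.** **1. Order of events.** Protocol 8.1 requires randomisation at least 24 hours before RFA. Protocol 8.2 and 8.4 start RFA 15 (+5) minutes after the infusion begins. Dwell time accrues after that. Both variables follow assignment and the start of study drug.

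**2. Can the arm affect them?** The protocol describes two plausible routes, neither shown to occur.

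- Section 6.2.4 names infusion reactions as a ThermoDox risk. Section 8.5.2 has the infusion slowed for mild reactions, and stopped with withdrawal from study treatment for worse ones. This falls around the time RFA is due.
- Section 6.2.4 says ThermoDox with RFA may enlarge the ablation volume. Section 8.4 lets a cycle end on temperature or impedance and has adequacy checked by imaging during the procedure. Dwell time could respond to the drug even with blinded operators.

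**3. Who has no value?** SAP section 2 defines ITT as everyone randomised, and As-Treated separately as those who received RFA with study infusion. Randomised subjects without RFA are therefore foreseen.

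**4. The plan's own event count.** Inputs from SAP 6.1.4: "overall 1-sided type 1 error of 0.025"; "detect with 80% power a hazard ratio for OS of 0.67"; "using a 1:1 treatment allocation (TR:PR) of 550 subjects"; "a target of 197 events (deaths) will be required for the primary analysis".

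Schoenfeld: 4 × (1.960 + 0.842)² / (ln 0.67)² = 4 × 7.849 / 0.1604 = 196 deaths. Freedman's formula gives 202. The planned 197 is reproduced.

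Power at 197: Φ(√197/2 × 0.4005 − 1.960) = Φ(0.851) = 80.2%. With the two O'Brien-Fleming-type looks it is 79.3%.

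**5. Loss of subjects and deaths.** The documents give no rate of non-ablation. Assume 1-3%, with the overall death fraction of 197/550:

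- Subjects: 550 × 0.01 = 5.5 to 550 × 0.03 = 16.5, so about 6-17.
- Deaths: × 197/550 = 2.0 to 5.9, so about 2-6.
- Fixed-design power: at 195 deaths Φ(0.836) = 79.8%; at 191 deaths Φ(0.807) = 79.0%.

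Larger assumed losses, as could arise under item e: 5% of deaths lost (187 left) gives 78.2%; 10% (177) 76.0%; 20% (158) 71.0%.

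**6. Bias, illustration only.** The assumptions are not from the documents: 20% of subjects have a poor prognosis, with 1.5, 2 or 3 times the hazard of the rest, and everyone removed comes from that group. Control median is 54 months, accrual 36 months and analysis at 66 months, with 3% per year loss. The true hazard ratio is 1.00; before removal the simulated value is 1.003-1.004.

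| Removed, ThermoDox / control | HR at 1.5× | HR at 2× | HR at 3× |
|---|---|---|---|
| 5% / 0% | 0.985 | 0.972 | 0.953 |
| 10% / 0% | 0.965 | 0.937 | 0.898 |
| 0% / 5% | 1.021 | 1.035 | 1.056 |
| 5% / 5% | 1.003 | 1.003 | 1.004 |

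Equal removal leaves the hazard ratio in place but costs 6-9% of deaths. In this illustration, bias needs removal that differs by arm, and its sign depends on which arm loses more.

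**The case against.** The strongest reply is that nothing decisive rests on these analyses. They are supportive, no decision rule uses them, and the interaction work is already called exploratory. The trial is double blind, and both arms share the start window and the 45-minute minimum, which limits operator-driven differences. Item e openly excludes subjects, and SAP 6.2.2 presents its criteria as a measure of adherence, so few readers would take it for ITT. The likely loss of deaths is small, and the protocol prespecified the RFA times.

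Much of this stands. The scope is supportive only, and item e needs splitting and a label rather than removal. What does not stand is the ITT status of items b-d. Prespecifying a variable does not make it a baseline variable. Blinding restrains the operator's choices, but not the drug's own effect on the infusion or on tissue.

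A reader might go further and infer that red urine unblinds operators and so shifts RFA timing. Protocol 6.2.4 places the discolouration in the 1 to 2 days after dosing, while RFA starts within 20 minutes of the infusion and must finish within 3 hours. It is not a credible influence on the first procedure. A reader might also infer that the plan repeats the post hoc dwell-time finding of the previous trial. It does not: here at least 45 minutes is required of every subject in both arms, and the SAP split is prespecified at 90 minutes.

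**Conclusion.** The point holds for SAP 6.3.2 items b-d and, through 6.3.3, for PFS. The subgroup hazard ratios by start and dwell time are not ITT comparisons. The adjusted treatment effect is not one either if selection retains these variables, or if the selection run drops subjects lacking them. Item e combines entry deviations with procedural ones, so it answers neither an eligibility question nor an adherence question cleanly.

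Three stronger readings are not supported:

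- That the primary result is compromised. SAP 6.3.1 uses all ITT subjects and the strata as randomised.
- That the adjusted model must condition on RFA times. It does so only if selection keeps them.
- That item e removes never-ablated subjects. Such a subject does not literally meet MRD6 or MRD7 and may stay in; the SAP is silent.

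The size and direction of any bias cannot be derived from the documents. The figures of 6-17 subjects and 2-6 deaths rest on the assumed 1-3%, and the hazard ratios in the table rest on the assumed prognosis and removal pattern. The change is worth making because it is cheap and settles how these results may be read.

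**What to change.** - **Items b-d:** limit the adjusted model and the ITT subgroups to factors fixed before randomisation: the stratification factors as randomised, age, race, region, aetiology, AFP and the protocol's baseline platelets. Include device only if it is chosen before randomisation, since protocol 8.3 lets an operator use more than one.
- **RFA start and dwell time:** report separately by randomised arm among ablated subjects, labelled exploratory and not ITT, with cut-points for start time and counts by arm of subjects without RFA. The As-Treated population is not a suitable home, because it groups subjects by treatment received and so gives up randomised assignment.
- **Item e:** run it twice, once excluding MRD1-5 only and once excluding MRD1-7 labelled per-protocol. State how never-ablated subjects are handled in each.
- **PFS:** apply the same wording through SAP 6.3.3.

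The cost is SAP text and one more run of item e for each endpoint. Dwell-time results move to exploratory status, and the departure from protocol 15.3.2.2, which names both RFA times, must be documented.
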